7.3.1.1. Time period and Frequency for collecting AE and SAE information

- Any SAEs assessed as related to study participation (e.g., protocol-mandated procedures, invasive tests, or change in existing therapy) or related to a GSK product will be recorded from the time a subject consents to participate in the study up to and including any follow-up contact.
- AEs will be collected from the start of Study Treatment until the follow-up contact. Refer to Section 7.3.1.3.
- Medical occurrences that begin prior to the start of study treatment but after obtaining informed consent may be recorded on the Medical History/Current Medical Conditions section of the CRF.
- All SAEs will be recorded and reported to GSK within 24 hours, as indicated in [Appendix 4](#).

- Investigators are not obligated to actively seek AEs or SAEs in former study subjects. However, if the investigator learns of any SAE, including a death, at any time after a subject has been discharged from the study, and he/she considers the event reasonably related to the study treatment or study participation, the investigator must promptly notify GSK.

NOTE: The method of recording, evaluating and assessing causality of AEs and SAEs plus procedures for completing and transmitting SAE reports to GSK are provided in [Appendix 4](#).

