10.4. Appendix 4: Treatment States and Phases

10.4.1. Treatment State and Study Phases

Assessments and events will be classified according to the time of occurrence relative to study visit or the start and/or stop date/time of the study treatment.

Treatment State	Study Phase
Pre-Treatment	Screening assessments collected prior to the Day 1 visit
On-Treatment	Period 1 and Period 2
Follow-up	Follow-up Visit

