10.4.1.1. Treatment States for AE, SAE and Concomitant Medications Data

Treatment State	Definition
Screening	AE(SAE or conmed) Start Date/Time < Study Treatment Start Date/Time. Based on the protocol, these AEs and concomitant medications prior to dosing will not be collected in database, and only record in the source document, but SAE will be captured on the dataset
Treatment A	If AE (SAE or conmed) onset date/time is on or after Period 1 treatment start date/time & before Period 2 treatment date/time Study Period 1 Treatment Start Date/Time ≤ AE Start Date/Time < Study Period 2 Treatment Date/Time]
Treatment B	If AE (SAE or conmed) onset date/time is on or after Period 2 treatment start date/time & before Study Conclusion date/time Study Period 2 Treatment Start Date/Time ≤ AE Start Date/Time < Study follow-up visit Date/Time]
Follow-up	All unsolved AEs (SAE or conmed) during the follow-up will be associated with the treatment from Period 2, and no AEs (SAE or conmed) will be report under the follow-up
Onset Time Since First Dose (Days)	If Treatment Start Date/Time > AE Onset Date/Time = AE Onset Date - Treatment Start Date If Treatment Start Date/Time ≤ AE Onset Date/Time = AE Onset Date - Treatment Start Date +1 Missing otherwise
Duration (Days)	AE Resolution Date – AE Onset Date + 1
Drug-related	If relationship is marked 'YES' on eCRF

NOTES:

- If the study treatment stop date is missing then the AE will be considered to be On-Treatment.

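### SAP 10.4.1.1 ends the Treatment B adverse-event window at two different, exclusive points, so a resolved event that starts at the follow-up visit can belong to no treatment

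*SAP*

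**What the plan says.** SAP 10.4.1 sets the principle: "Assessments and events will be classified according to the time of occurrence relative to study visit", or to the start or stop of study treatment. Classification is therefore by occurrence, not by detection.

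The Treatment B row of SAP 10.4.1.1 states its window twice:

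- in words, onset "on or after Period 2 treatment start date/time & before Study Conclusion date/time";
- as a formula, "Study Period 2 Treatment Start Date/Time ≤ AE Start Date/Time < Study follow-up visit Date/Time".

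The next row deals with follow-up by sending unresolved events to the Period 2 treatment. It then rules out a separate category: "no AEs (SAE or conmed) will be report under the follow-up".

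Protocol 7.3.1.1 defines what is collected. For AEs: "AEs will be collected from the start of Study Treatment until the follow-up contact". For SAEs related to study participation or to a sponsor product, recording runs from consent "up to and including any follow-up contact".

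Protocol 4.2 places laboratory tests, vital signs and a 12-lead ECG at the follow-up visit, and Protocol 5.5 makes that visit part of completing the study. SAP Appendix 11 presents all AEs (Table 2.3) and drug-related AEs (Table 2.4) by treatment, and lists all AEs in Listing 10.

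**The concern.** One window with two end points can be programmed in two ways. The formula is the version a programmer is most likely to code, and it shuts at the moment of a visit that can itself generate AEs. Protocol 12.4.1 counts a clinically significant laboratory or ECG abnormality as an AE. If such a finding is dated to the visit, it fails the strict inequality. The Follow-up row then catches it only if it is *unsolved*, and the table offers no other column.

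At stake is the completeness of the Treatment B column in Tables 2.3 and 2.4, and their agreement with Listing 10. Safety of cabotegravir alone and with rifabutin is a secondary objective. Some of the named risks, neutropenia and transaminase elevation, are found by laboratory test.

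**Working it through.** The plan states no figure on this point, so the check applies its rules to typical cases.

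**Inputs.** Last dose on Day 28 and follow-up about 10 to 14 days later (Protocol 4.2), so the visit falls between Day 28 + 10 = 38 and Day 28 + 14 = 42. Period 2 starts on Day 15. The rules are those of SAP 10.4.1.1. The clock times are assumed, because the documents give none: visit at 09:00, study conclusion recorded at 11:00 the same day.

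**Rules applied in order.** (i) Onset on or after Day 15 and before the end point: Treatment B. (ii) Otherwise, if unresolved: Treatment B through the Follow-up row, read as covering new events. (iii) Otherwise: no state.

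| Onset | Status | End point = follow-up visit (formula) | End point = study conclusion (words) |
|---|---|---|---|
| 3 days before the visit, first reported there | either | B | B |
| At the visit time, or 1 hour into it | unresolved | B via Follow-up row | B |
| At the visit time, or 1 hour into it | resolved | **none** | B |
| 1 day after the visit | unresolved | B via Follow-up row | B via Follow-up row |
| 1 day after the visit | resolved | none | none |

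Results are the same for Day 38 and Day 42. The last two rows lie beyond the protocol's AE collection window and are not part of the point. The third row is the gap, and there the two end points give different answers.

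**Two things that move the boundary.**

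1. *Dates without times.* If only dates are compared, an onset on the visit date gives 38 < 38, which is false. Any event starting that calendar day then depends on the Follow-up row. If study conclusion carries the same date, the verbal end point fails in the same way.
2. *When resolution is judged.* Protocol 7.3.6 has clinically significant laboratory abnormalities, during the study or within 14 days after the last dose, repeated until they return to normal or baseline. A finding at the follow-up visit can therefore be open that day and closed by database freeze. The SAP does not say which status decides, so two events with the same onset could be counted differently.

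**Against the protocol.** A related SAE starting at the follow-up contact is inside the protocol's window and outside the formula. For other AEs the protocol says only that collection runs until that contact, so the conflict is explicit for related SAEs and arguable for the rest.

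**The case against.** The strongest reply is that the Follow-up row shows an intention to fold late events into Treatment B. A laboratory abnormality seen at the visit will normally still be open that day, so the row would catch it. The verbal end point also covers onset during the visit if conclusion is recorded afterwards. Both points stand, and they make the gap narrow. They do not close it: the verbal end point contradicts the formula, and the row makes assignment depend on resolution. The row could also be read as covering only events carried over from before the visit. On that reading, every new-onset event at the visit would be outside the formula.

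A reader might infer more than the documents support:

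- *That any AE first found at the follow-up visit is lost.* It is not. Both statements of the window use onset, so an event that began earlier is in Treatment B.
- *That safety signals would be hidden.* SAP 10.4.1.2 gives other safety data a Follow-up slice. Haematology, chemistry and ECG are summarised by treatment and time (Tables 2.8, 2.9, 2.17 to 2.20), Table 2.25 lists liver events, and Listings 10 to 12 keep all AEs, chemistry and haematology.
- *That the loss can be sized* by counting follow-up assessments, or as one subject in 15. Neither measures AEs lost.

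No passage says that a laboratory or ECG event takes the sample or tracing time as its onset. That is a natural convention for a symptomless finding, but it is an assumption here.

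**Conclusion.** The point holds in a narrow form. The Treatment B row is internally inconsistent. Under its formula together with the Follow-up row, an AE or SAE with onset at the follow-up visit that has since resolved has no treatment and no place in Tables 2.3 and 2.4. This is an error in a stated rule rather than a missing detail, because literal programming would undercount Treatment B events and put the tables at odds with the listing.

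Severity is minor. The safety tables are descriptive, the listing retains the events, and the documents give no basis for saying how many AEs would be affected; it may be none. The conclusion assumes that such events are dated to the visit and that the formula is what is programmed.

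**What to change.** In SAP 10.4.1.1:

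1. Replace both Treatment B end points with one inclusive rule: onset on or after the Period 2 treatment start and on or before the follow-up contact or study conclusion date. Name which of the two is used, and say whether dates or date/times are compared.
2. Reword the Follow-up row so that all AEs and SAEs with onset after the Period 2 start are assigned to Treatment B, resolved or not. The existing statement that nothing is reported under follow-up can then stay. The same rows govern concomitant medications, so apply the wording there too.

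The cost is a short SAP edit and a matching change to the treatment-state derivation. No new data are needed.

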4.2. Treatment Periods and Duration

Subjects will undergo a screening visit within 30 days of the first dose of study drug, followed by two treatment periods and a follow-up period.

Subjects will undergo clinical safety assessments and serial PK assessments at time-points specified in Section 7.1, Time and Events table of the protocol.

Period 1

Eligible participants will be admitted to the unit on Day -1.

On Day 1, following completion of the required pre-dose measurements, the investigator or authorized study unit personnel will administer a single oral dose of 30 mg CAB to each subject in the unit.

Subjects will be dispensed a bottle of CAB to be taken at home on Days 2-12 and discharged from the unit. Subjects will be provided with a subject diary to document daily recordings of dosing occurring outside of the unit. Subjects will be re-admitted to the unit in the morning on Day 13. Prior to dosing, a CAB PK sample will be obtained, and then the subjects will receive a single 30 mg dose of CAB on Day 13 and remain in the unit overnight. On Day 14, following an overnight fast of at least 6 hours, subjects will receive a single 30 mg dose of CAB with serial CAB PK samples collected pre-dose and through 24 hours after dosing up to Day 15. There will be no washout between Period 1 and Period 2.

Period 2

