On Day 15 following the completion of the required Day 14 safety assessments and PK collection, subjects will proceed to Period 2, where site staff will administer a single dose of RBT 300 mg and a single dose of CAB 30 mg in the unit. Subjects will be discharged and dispensed a bottle of RBT and a bottle of CAB to be taken at home on Days 16-20. Subjects will be provided with a subject diary to document daily recordings of home dosing. In the morning of Day 21, subjects will bring their bottle of RBT and bottle of CAB for observed dosing in the unit and safety assessments as an outpatient visit. Following these procedures, subjects will be discharged with their supply of CAB and RBT and instructed to take their daily doses of study medications at home in the mornings of Days 22 through 25. On Day 26, subjects will return to the unit for a pre-dose PK collection and observed dosing as an outpatient visit and then be discharged home. On Day 27, subjects will be re-admitted to the unit for a pre-dose PK collection, observed dosing, and safety assessments then remain in the unit overnight. In the morning of Day 28 following an overnight fast of at least 6 hours, subjects will receive a single dose of RBT and a single dose of CAB in the unit with serial CAB PK samples collected pre-dose and through 24 hours after dosing up to Day 29. Subjects will be discharged from the unit on Day 29 after the final assessment is completed. Subjects will complete a follow-up visit ~ 10-14 days after the last 30 mg oral dose of CAB.

At the follow-up visit, laboratory safety assessments (including pregnancy test for females of childbearing potential) will be performed, and vital signs together with a 12-lead ECG will be obtained.

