
Hypersensitivity Reactions (HSR)
	
Hypersensitivity reactions have been reported as uncommon occurrences with integrase inhibitors, including the closely related compound dolutegravir, and were characterized by rash, constitutional findings, and sometimes, organ dysfunction, including liver injury.
 
While there have been no clinical cases of hypersensitivity to CAB, there is a theoretical risk of systemic or severe hypersensitivity reactions with or without hepatic symptoms.
	
 • Clinical assessments, laboratory tests (including liver transaminases) and vital signs will be performed throughout this study (refer to Time & Events Table). Results from these assessments may aid early detection of HSR. • Oral CAB will be withdrawn immediately for cases with suspected HSR. Any HSR reactions that occur would be managed supportively.

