9.4. Key Elements of Analysis Plan

Final analysis will be performed after the completion of the study and final datasets authorization.

Data will be listed and summarized according to GlaxoSmithKline reporting standards, where applicable. Listings will be sorted by subject, period, day, and time, noting treatment; summaries will be presented by treatment, day, and time.

Unless stated otherwise, descriptive summaries for continuous variables will include n, mean, standard deviation (SD), coefficient of variation for the mean (%CV), median, minimum, and maximum, geometric mean with associated 95% confidence interval (CI), and the between-subject CV (%CVb) for the geometric mean; whereas, n and percent will be used as summary statistics for categorical variables.

Baseline or pre-dose assessment is the last available assessment prior to time of the first dose unless it is specified otherwise. If there are multiple assessments collected on the same scheduled time, the average of these assessments will be used. For tabulated safety summaries, only the scheduled assessments will be included in the summary tables.

Version 9.3 or higher of the Statistical Analysis Software (SAS) system will be used to analyze the data as well as to generate tables, figures, and listings.

Complete details will be documented in the Reporting and Analysis Plan (RAP).

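### The SAP's Follow-up row has no onset condition, so an adverse event that began on cabotegravir alone and is still open at follow-up can be counted under rifabutin plus cabotegravir

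*SAP*

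**What the plan says.** SAP 10.4.1 gives the general principle: "Assessments and events will be classified according to the time of occurrence relative to study visit", or relative to the start and stop of study treatment.

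SAP 10.4.1.1 applies it to adverse events, SAEs and concomitant medications.

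- **Treatment A row:** an event belongs here if its "onset date/time is on or after Period 1 treatment start date/time & before Period 2 treatment date/time".
- **Treatment B row:** an event belongs here if its "onset date/time is on or after Period 2 treatment start date/time & before Study Conclusion date/time". The formula beneath this text sets the upper limit as strictly earlier than the follow-up visit.
- **Follow-up row:** "All unsolved AEs (SAE or conmed) during the follow-up will be associated with the treatment from Period 2". The same sentence then rules out any separate reporting under follow-up.

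The design is a fixed sequence, A then B, and Protocol 4.2 states: "There will be no washout between Period 1 and Period 2". It also states: "Subjects will complete a follow-up visit ~ 10-14 days after the last 30 mg oral dose of CAB". Protocol 9.4 says that "summaries will be presented by treatment, day, and time", and SAP 10.11.4 lists Table 2.3 (all adverse events) and Table 2.4 (drug-related adverse events) as by-treatment summaries.

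**The concern.** The Treatment A and B rows sort events by when they began. The Follow-up row sorts them by whether they have ended, and it covers all such events. The two criteria can disagree for one kind of event: onset in Period 1 and still unresolved at follow-up. The SAP does not say which row then wins. SAP 10.5.3 defaults to reporting by the treatment actually received, but that does not settle the matter, because a subject who continues into Period 2 has received both.

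Such events are possible under the protocol. There is no washout, and Appendix 7 lets a subject with Grade 1 or Grade 2 rash stay on study drug at the investigator's discretion. Suspected hypersensitivity is different and should not carry into Period 2, since "Oral CAB will be withdrawn immediately for cases with suspected HSR".

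Safety and tolerability of CAB alone and in combination is a stated secondary objective. Two programmers could place the same open event under different treatments and each point to a row of the SAP. Because every subject takes A before B, any event moved by this row moves from CAB alone to RBT+CAB, never the other way.

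**Working it through.** The plan states no figure on this point, so the check is to apply the rows as written to test events.

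**Inputs.** Period 1 starts on Day 1, Period 2 starts on Day 15 and the last dose is on Day 28 (Protocol 4.2). Follow-up is 10 to 14 days after the last dose: 28 + 10 = Day 38 to 28 + 14 = Day 42. For the test events the visit is assumed to fall on Day 40 (28 + 12). The Treatment B row is applied by its formula.

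**Rules.**
- Treatment A: Day 1 ≤ onset < Day 15.
- Treatment B: Day 15 ≤ onset < Day 40.
- Follow-up: unresolved at Day 40, assigned to Treatment B.

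| Onset | Resolved | Rows met as written | With the Follow-up row limited to onset from Day 15 |
|---|---|---|---|
| Day 5 | Day 10 | A | A |
| Day 5 | Day 20 | A | A |
| Day 5 | still open | A, and Follow-up (to B) | A |
| Day 20 | Day 25 | B | B |
| Day 20 | still open | B, and Follow-up (to B) | B |
| Day 33 | still open | B, and Follow-up (to B) | B |
| Day 40 (at the visit) | still open | Follow-up (to B) only | B |

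Only the third event gets conflicting assignments. The limit on onset resolves it to Treatment A and leaves the other six where they were. The last line shows that the Follow-up row does useful work, because the strict upper limit in the Treatment B formula leaves out an event that begins at the follow-up visit.

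**How long such an event must last.** With onset on Day 10, it has been open for 38 − 10 = 28 to 42 − 10 = 32 days by follow-up.

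**Size per event.** With 15 subjects dosed, one subject is 1/15 = 6.7 percentage points in that event's row. If only 12 reach Period 2 (an assumption, from the planned number of completers), one subject under Treatment B is 1/12 = 8.3 points. If the event is moved, A falls and B rises by these amounts. If it is counted under both, only B rises. The any-event row changes for a treatment only if the subject has no other event there.

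**The case against.** The best defence is that the row has an innocent purpose. Its second half says that there is no follow-up reporting category, so the first half may only explain where the remaining events go. The row also has a real function on that reading: laboratory tests, vital signs and an ECG are done at the follow-up visit, and an event first found there falls outside the Treatment B formula. With the time-of-occurrence principle in SAP 10.4.1 and an onset-defined Treatment A row, assignment by onset is a coherent reading and quite possibly the intended one.

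This stands as an account of intent, but it does not cure the wording. The row covers all unresolved events, not only those that begin at the follow-up visit, and nothing else in either document narrows it.

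The argument on impact also stands. The case needs an event open for about a month in a healthy volunteer. No hypothesis is tested, and no formal safety contrast between treatments is planned. Every adverse event is listed individually (Listing 10), with onset time and duration derived, so a misplaced event could be traced.

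A reader might go further in three directions that the documents do not support.

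- **Worsening in Period 2.** One might infer that a Period 1 event that worsens on RBT+CAB would be hidden under CAB alone. That depends on how sites record worsening, and the CRF instructions are not in the documents. Protocol 12.4.5 puts updates in the original CRF, but Protocol 12.4.1 counts increased intensity of a pre-existing condition as an adverse event.
- **Table 2.24.** One might infer that the rule interacts with its threshold of more than 5%. At this sample size one subject always exceeds it (1/15 = 6.7%), so the threshold removes nothing and the point only restates a count of one against zero. Unlike Tables 2.3 and 2.4, its title does not mention treatment.
- **Table 2.6.** No defect can be shown. It is already a listing by subject and treatment.

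**Conclusion.** Wrong as written, minor. The Follow-up row conflicts with the onset rule for Period 1 events still open at follow-up. Read literally, it charges them to RBT+CAB in Tables 2.3 and 2.4. Each affected subject is worth 6.7 percentage points with 15 dosed, or 8.3 under Treatment B if 12 reach Period 2, always in the direction of the combination.

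A reader might infer that misassignment, and hence a biased safety comparison, is certain. The documents do not support that: the programmer may follow the onset rows, and the documents do not say how often such an event would occur. What is established is an unresolved conflict between rows. It touches descriptive safety displays only. PK analyses do not use these rows, and laboratory, ECG and vital-sign data are summarised by visit under SAP 10.4.1.2.

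**What to change.** In SAP 10.4.1.1, limit the Follow-up row by onset and state what happens to the rest. Suggested text:

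*Adverse events, SAEs and concomitant medications with onset on or after the first Period 2 dose, including onset at the follow-up visit, are reported under Treatment B. Those with onset in Period 1 stay under Treatment A even if unresolved at follow-up. There is no separate follow-up category.*

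This keeps the row's useful function and removes the overlap. It costs one or two lines, best added before the adverse event tables are programmed. It needs no new assessment and no change to data collection.

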3. OBJECTIVES AND ENDPOINTS

Primary	

 To compare steady state CAB exposure following 30 mg oral dose once daily with and without RBT 300 mg once daily. 	
 Plasma CAB_AUC(0-τ), C_{max}
Secondary	

 To describe the pharmacokinetic (PK) of CAB 30 mg oral dose once daily administered alone and co-administered with RBT. 	
 Plasma CAB_Cτ, t_{max}, t_{1/2}, CL/F

 To assess the safety and tolerability of CAB 30 mg oral dose administered alone and in combination with RBT 300 mg once daily. 	
 Safety and tolerability parameters, including adverse events, concurrent medication, clinical laboratory screens, electrocardiogram (ECG), and vital signs assessments.

AUC_(0-t) = area under the plasma concentration time curve from time zero to the last quantifiable time point C_{max} = maximum observed concentration C_t = last quantifiable concentration t_{max} = time of maximum observed concentration t_{1/2} = the elimination half-life
 
 CL/F = apparent oral clearance 	

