4. STUDY DESIGN

4.1. Overall Design

This study is a phase I, single-center, open label, fixed-sequence, 2-period crossover study in healthy adults to evaluate the effect of RBT on the PK of oral CAB 30 mg.

Table 1 Study Design

Subjects	Screening Period	Period 1 Days 1 – 14	Period 2 Days 15 - 28	Follow-up
N=15	Within 30 Days of Day 1	Treatment A	Treatment B	~10-14 days after last dose of CAB

 Treatment A = CAB 30 mg once daily x 14 days Treatment B = RBT 300 mg once daily + CAB 30 mg once daily x 14 days 				

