10.11.4. Safety Tables

Safety Tables					
No.	Population	IDSL / TST ID / Example Shell	Title	Programming Notes	Deliverable [Priority]
Adverse Events					
2.1.	Safety	LAI117010/ Table 2.1	Summary of Exposure Data	By subject and treatment	SAC
2.2.	Safety	LAI117010/ Table 2.2	Relationship of Adverse Event System Organ Classes, Preferred Terms, and Verbatim Text		SAC
2.3.	Safety	LAI117010/ Table 2.3	Summary of All Adverse Events by Treatment		SAC
2.4.	Safety	LAI117010/ Table 2.4	Summary of Drug-Related Adverse Events by Treatment		SAC
2.5.	Safety	LAI117010/ Table 2.5	Listing of Serious Adverse Events	By subject and treatment.	SAC
2.6.	Safety	LAI117010/ Table 2.6	Listing of Adverse Events Leading to Permanent Discontinuation of Study Drug or Withdrawal from Study	By subject and treatment	SAC
Labs					
2.7.	Safety	LAI117010/ Table 2.7	Listing of Reference Ranges for Clinical Laboratory Tests		SAC
2.8.	Safety	LAI117010/ Table 2.8	Summary of Clinical Haematology Laboratory Data by Treatment and Time		SAC
2.9.	Safety	LAI117010/ Table 2.9	Summary of Clinical Chemistry Laboratory Data by Treatment and Time		SAC
2.10.	Safety	LAI117010/ Table 2.10	Summary of Treatment Emergent Grade 2 or Higher Lab Abnormalities by Treatment	Summary of Treatment Emergent Lab toxicity only.	SAC
2.11.	Safety	LAI117010/ Table 2.11	Listing of Treatment Emergent Grade 2 or Higher Lab Abnormalities	By subject and treatment	SAC
2.12.	Safety	CP_LB5	Summary of All Urinalysis Data		SAC

Safety Tables					
No.	Population	IDSL / TST ID / Example Shell	Title	Programming Notes	Deliverable [Priority]
Vital Signs					
2.13.	Safety	LAI117010/ Table 2.13	Summary of Vital Signs by Treatment and Time	Include BP and HR only.	SAC
2.14.	Safety	LAI117010/ Table 2.14	Summary of Change from baseline in Vital Signs by Treatment and Time	Include BP and HR only.	SAC
2.15.	Safety	LAI117010/ Table 2.15	Listing of Vital Signs for Subjects with Abnormalities of Potential Clinical Importance	By subject and treatment	SAC
ECGs					
2.16.	Safety	LAI117010/ Table 2.16	Summary of ECG Findings		SAC
2.17.	Safety	LAI117010/ Table 2.17	Summary of ECG Values by Treatment and Time		SAC
2.18.	Safety	LAI117010/ Table 2.18	Summary of Change from Baseline in ECG Values by Treatment and Time		SAC
2.19.	Safety	LAI117010/ Table 2.19	Summary of Category of QTc Data by Treatment and Time		SAC
2.20.	Safety	LAI117010/ Table 2.20	Summary of Category of QTc Change from Baseline by Treatment and Time		SAC

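### Treatment B collects adverse events over 23–27 days and Treatment A over 14, and the by-treatment AE tables do not correct for the difference

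*SAP*

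**What the plan says.** One secondary objective is "To assess the safety and tolerability of CAB 30 mg oral dose administered alone and in combination with RBT 300 mg once daily" (Protocol section 3). The main AE displays for it are Table 2.3, "Summary of All Adverse Events by Treatment", and Table 2.4, its counterpart for drug-related events (SAP 10.11.4).

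SAP 10.4.1.1 decides which column an event enters:

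- **Treatment A:** "onset date/time is on or after Period 1 treatment start date/time & before Period 2 treatment date/time".
- **Treatment B:** "Study Period 2 Treatment Start Date/Time ≤ AE Start Date/Time < Study follow-up visit Date/Time". The same row also names study conclusion as the end point, so it gives two descriptions of where B stops.
- **Follow-up:** events unresolved during follow-up "will be associated with the treatment from Period 2, and no AEs (SAE or conmed) will be report under the follow-up".

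The Treatment B row matters most here, because it brings new onsets after the last dose into B. The Follow-up row covers only events still unresolved, and confirms that no separate category is reported.

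On timing, the design table gives "Period 2 Days 15 - 28" (Protocol 4.1). Protocol 4.2 states "There will be no washout between Period 1 and Period 2" and "Subjects will complete a follow-up visit ~ 10-14 days after the last 30 mg oral dose of CAB". Protocol 7.3.1.1 collects AEs from the start of treatment to the follow-up contact, so new events are recorded throughout the interval after Day 28.

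Elsewhere the SAP keeps follow-up apart. SAP 10.4.1 lists it as a state distinct from on-treatment, and 10.4.1.2 gives it its own time slice for the other safety data.

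**The concern.** The two columns of Tables 2.3 and 2.4 cover different lengths of observation. Treatment A has no time after dosing, because Period 2 starts at once. Treatment B has its dosing period plus the interval to the follow-up visit. If any AEs start in that interval, whether drug-related or background, they can only raise the B column. The SAP lists no exposure-adjusted rate, follow-up column or footnote that would tell a reader so.

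The exposure table will not reveal the difference. SAP 10.6.2 computes exposure from treatment start and stop dates, which gives about 14 days for each treatment beside AE windows that are unequal. A reader would naturally take the percentages as covering equal time.

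The treatment of one interval is also inconsistent: a laboratory value from the follow-up visit is summarised under Follow-up, while an AE that starts shortly before it is counted under RBT + CAB.

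**Working it through.** **Check on the calendar.** The plan states no AE window length. Its nearest figure is the overall duration of about 10 weeks (Protocol synopsis): 4 + 2 + 2 + 2 = 10 weeks. It reproduces.

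**Window lengths**, from the onset rules and visit days above:

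- A: Day 1 dose to Day 15 dose = 15 − 1 = 14 days.
- Follow-up visit: Day 28 + 10 to 14 = Day 38 to Day 42.
- B: 38 − 15 = 23 days, to 42 − 15 = 27 days. That is 14 days of dosing plus a tail of 9 to 13 days.
- Ratio B/A: 23/14 = 1.64 to 27/14 = 1.93.
- Exposure by the SAP formula, all doses taken: A = 14 − 1 + 1 = 14 days; B = 28 − 15 + 1 = 14 days.

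**What equal hazards would produce.** The documents give no AE rate, so the 14-day incidence in A, *p*, is an assumption shown over a range. With a constant hazard that is the same in both periods and after dosing, the expected incidence in B over *d* days is 1 − (1 − *p*)^(*d*/14).

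| Assumed incidence in A | B, 23 days | B, 27 days | Ratio B/A |
|---|---|---|---|
| 10% | 15.9% | 18.4% | 1.59–1.84 |
| 20% | 30.7% | 35.0% | 1.53–1.75 |
| 30% | 44.3% | 49.7% | 1.48–1.66 |
| 50% | 68.0% | 73.7% | 1.36–1.47 |

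With 12 subjects and 20% in A, that is 2.4 subjects expected in A and 3.7–4.2 in B, with no true difference.

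**Lower hazard after dosing.** If the hazard in the tail is half as high, the effective window for B is 14 + 9/2 = 18.5 to 14 + 13/2 = 20.5 days. Then 20% in A becomes 1 − 0.8^(18.5/14) = 25.5% to 1 − 0.8^(20.5/14) = 27.9%, or about 3.1–3.3 of 12 subjects against 2.4. If no events start in the tail, the difference disappears.

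**After the fix.** Cutting at Day 29, 24 hours after the Day 28 dose, gives 29 − 15 = 14 days for B. The ratio to A is 1.00, with 9–13 days left in the follow-up part.

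**The case against.** The best defence is that keeping B open to the follow-up visit is a deliberate, conservative choice. Half-lives are about 38 hours for RBT and 40 hours for CAB (Protocol 4.5), so five half-lives last 5 × 38/24 = 7.9 and 5 × 40/24 = 8.3 days. Most of the 9–13 day tail therefore carries residual exposure. Protocol 4.6.2 also says that uveitis can appear from 2 weeks after RBT is started, which is Day 29, exactly where a 14-day window would close. Removing every later onset from the combination would under-attribute a named RBT risk. This stands. A reader might infer that tail events are simply off-treatment and do not belong to B; the documents do not support that. It does not equalise the windows, though: A has no tail, and late effects of CAB taken alone also fall into B.

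Other points that stand:

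- Tables 2.3 and 2.4 are not the only tolerability displays. Laboratory, ECG and vital-sign data are also summarised by treatment, and the full AE listing with derived onset day should let a reader find the late events.
- The fixed sequence already confounds treatment with period and with cumulative CAB exposure. Equal windows would not make A against B an unbiased comparison.
- No hypothesis is tested and about 12–15 subjects are involved. With half the hazard in the tail, the shift is under one subject in 12.

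A reader might also infer that events in subjects who leave during Period 1 will be counted under B. The rules do not require this: B needs an onset on or after a Period 2 dose, and SAP 10.5.3 reports data by the treatment actually received. What remains is loose wording, since A has no defined end for such a subject and the Follow-up row points to a treatment never taken.

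SAP 10.4.1 is a general scheme and 10.4.1.1 the specific AE rule, so the difference between them is untidy and not a strong contradiction.

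**Conclusion.** The concern holds as a limited point about presentation and interpretation. The imbalance of 14 against 23–27 days follows from the documents alone, subject only to the follow-up visit being approximately timed. Nothing in the planned AE tables corrects or discloses it, and any events that start in the tail can only add to the combination.

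The size in percentages is less certain. It rests on assumed AE rates and an assumed hazard after dosing, neither of which the documents give. The ratio of 1.64–1.93 applies to expected event counts under an equal constant hazard; the ratio of subject percentages is smaller, 1.36–1.84 over the range shown, and smaller again if the hazard falls after dosing. A reader might infer that the combination is bound to look clearly worse; with so few subjects and an unknown tail hazard, that goes too far.

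The effect is confined to a descriptive secondary safety comparison. The primary AUC(0-τ) and Cmax analysis is unaffected. The change is worth making because it is cheap and loses no information.

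**What to change.** In SAP 10.4.1.1 and Tables 2.3 and 2.4:

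1. Split Treatment B events by onset into on-treatment (first Period 2 dose to 24 hours after the Day 28 dose, 14 days, matching A) and follow-up (from then to the follow-up visit).
2. Keep the combined Treatment B total and an overall column, so that delayed RBT events and those under residual exposure stay visible under the combination.
3. Base any statement comparing AE incidence in A and B on the equal 14-day windows, and footnote the window lengths.
4. State one end point for Treatment B, in place of both study conclusion and the follow-up visit.
5. State that post-dose events in subjects who withdraw during Period 1 are assigned to Treatment A or its follow-up, in line with reporting by treatment received.

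The cost is one extra column, a footnote and slightly more table programming. No new data are needed and no event is dropped.
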